9.2.1. Analysis of the Primary Immunogenicity Objective

The assessment of the MnB immune response induced by bivalent rLP2086 will be performed by compiling the proportions of subjects (point estimate) in the bivalent rLP2086 + MenACWY-CRM vaccine groups (Group 2 – ACWY-naive and Group 4 – ACWY-experienced) for each MnB coprimary endpoint, along with the exact 2-sided 95% CI for each endpoint. The primary endpoints are defined as a 4-fold rise from baseline in hSBA titer as follows:

- For subjects with a baseline hSBA titer below the LOD (or an hSBA titer of <1:4), a 4-fold response is defined as an hSBA titer of $\geq 1:16$ or the LLOQ (whichever titer is higher).
- For subjects with a baseline hSBA titer of \geq LOD (ie, hSBA titer of $\geq 1:4$) and < LLOQ, a 4-fold response is defined as an hSBA titer of ≥ 4 times the LLOQ.
- For subjects with a baseline hSBA titer of \geq LLOQ, a 4-fold response is defined as an hSBA titer of ≥ 4 times the baseline titer.

The composite endpoint defined as

- the proportion of subjects achieving an hSBA titer \geq LLOQ (1:16 for A22 and 1:8 for A56, B24, and B44) for all 4 primary test strains combined.

If each of the LCIs meets or exceeds the associated target LCI ([Table 12](#)), then the null hypothesis will be rejected, and the study objective in terms of the immunogenicity will be met.

The evaluation for all 5 primary endpoints will also be performed for US subjects only.

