## 2. INTRODUCTION

This SAP provides the detailed methodology for summary and statistical analyses of the data collected in Study B1971057. A brief description of the study design and the study objectives are given. Subsequent sections include analysis population and the definitions of the immunogenicity and safety endpoints followed by details around statistical analysis and reporting. A list of tables, listings, and figures, mock-up tables, listings, and figures, and programming rules are prepared separately based on the methods described in this document. This document may modify the plans outlined in the protocol; however, any major modifications of the primary endpoint definition or its analysis will also be reflected in a protocol amendment.

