### **3. ENDPOINTS AND BASELINE VARIABLES: DEFINITIONS AND CONVENTIONS**

#### **3.1. Primary Endpoints**

##### **3.1.1. Primary Immunogenicity Endpoints**

Five coprimary endpoints are defined for the primary objectives; they are defined for hSBA performed with each of the 4 primary test strains: PMB80 (A22), PMB2001 (A56), PMB2948 (B24), and PMB2707 (B44).

- One of the 5 coprimary endpoints is the composite endpoint defined as the proportion of subjects achieving an hSBA titer  $\geq$  lower limit of quantitation (LLOQ: 1:16 for A22 and 1:8 for A56, B24, and B44) for all 4 primary test strains combined, 1 month after the second vaccination (Visit 4) in the bivalent rLP2086 arms (Group 2 and 4 subjects) combined.
- Four of the coprimary endpoints are defined as the proportion of subjects achieving at least a 4-fold increase in hSBA titer from baseline to 1 month after the second vaccination (Visit 4) in the bivalent rLP2086 arms (Group 2 and 4 subjects) combined for each of the 4 primary test strains.
  - For subjects with a baseline hSBA titer below the limit of detection (LOD, or an hSBA titer of  $<1:4$ ), a 4-fold response is defined as an hSBA titer of  $\geq 1:16$  or the LLOQ (whichever titer is higher).
  - For subjects with a baseline hSBA titer of  $\geq$  LOD (ie, hSBA titer of  $\geq 1:4$ ) and  $<$  LLOQ, a 4-fold response is defined as an hSBA titer of  $\geq 4$  times the LLOQ.
  - For subjects with a baseline hSBA of  $\geq$  LLOQ, a 4-fold response is defined as an hSBA titer of  $\geq 4$  times the baseline titer.

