**Table 14. Severity Scale for Fever for Stage 2**

38.0-38.4°C
>38.4-38.9°C
>38.9-40.0°C
>40.0°C

Temperatures <35.0°C and >42.0°C will be excluded from the analysis.

The original temperature scale (Table 13) was used in Stage 1 reporting and the updated temperature scale (Table 14) will be used in Stage 2 analyses.

For each systemic event, the following variables will be available similar to local reactions:

1. Each systemic event on each day (Days 1 to 7) after each vaccination.
2. Each systemic event on any day (Days 1 to 7) after each vaccination and any vaccination.
3. Any systemic event on any day (Days 1 to 7) after each vaccination and after any vaccination.
4. Maximum severity of each systemic event on any day (Days 1 to 7) after each vaccination and any vaccination.
5. Maximum duration of each systemic event after each vaccination.

The derivation of these variables is similar to the derivation of the variables for local reactions (Section 3.5.2.1).

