- = 0, if not all 4 MenB primary strains have assay results  $\geq$  LLOQ.

In [Section 6.4](#), a supportive analysis is included describing different handling of missing values for the composite response.

For MenB-related endpoints, the 4-fold response in assay titers from baseline (Visit 1 prevaccination) to 1 month after the second vaccination (Visit 4) will be defined as follows:

- For subjects with a baseline hSBA titer < LOD or an hSBA titer of <1:4, a 4-fold response is defined as an hSBA titer of  $\geq 1:16$  or the LLOQ (whichever titer is higher).
- For subjects with a baseline hSBA titer of  $\geq$  LOD (ie, hSBA titer of  $\geq 1:4$ ) and < LLOQ, a 4-fold response is defined as an hSBA titer of  $\geq 4$  times the LLOQ.
- For subjects with a baseline hSBA of > LLOQ, a 4-fold response is defined as an hSBA titer of  $\geq 4$  times the baseline titer.

The 4-fold response variable for the 4 MenB primary strains will be computed as:

= •, if the assay result at baseline or specific time point is missing, indeterminate, or otherwise unavailable;

= 1, if the assay result meets 1 of the 3 definitions for a 4-fold response;

= 0, if the assay result does not meet 1 of the 3 definitions for a 4-fold response.

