### **5.3. Methods to Manage Missing Data**

#### **5.3.1. Immunogenicity Data**

As assay data are expected to be missing completely at random, the primary analysis for the primary objectives will be based upon the observed, determinate observations. No imputation will be performed. The proportion of subjects with missing immunogenicity data may be summarized at each blood sampling visit for each primary MenB strain. The denominator will be the ITT population (all randomized). The category of missing reasons (quantity not sufficient [QNS], indeterminate, not done, dropout) may also be summarized. Similar summaries may also be performed to evaluate the proportion of missing hSBA-MenA, hSBA-MenC, hSBA-MenW, and hSBA-MenY titers.

If 10% or more of the subjects in any strata have missing hSBA data for the 4 primary MenB strains, a sensitivity analysis using mixed-effects model with repeated measures (MMRM) for Groups 2 and 4 will be applied for the primary MenB strains (GMT). The MMRM uses maximum likelihood estimation under the assumption that the missingness is at random (MAR). To account for the intrasubject correlation among the repeated measures, an unstructured covariance matrix will be used. In case the model does not converge, further covariance structures will be explored (ie, first-order autoregressive, compound symmetry).

$\text{Log (hSBA)} = \text{race} + \text{sex} + \text{geographic location (US; ex-US)} + \text{age at randomization} + \text{visit}$ .  
The intercept will be set as random effect.

Race categories other than White, Black, or Asian will be combined into a separate category termed "Other."

In addition to Type III analysis output, least-squares GMTs at each visit will be summarized for each strain.

These analyses will use the mITT population, using ½ LLOQ to impute the hSBA values below LLOQ for the primary strains only.

Similar to GMT, GLIMMIX will be utilized. The response variables are binary variables (composite response and 4-fold response) and a Logit link will be used. The model will be similar to the above. As 4 out of 5 endpoints (4-fold responses) will not have a response at Visit 1, the GLIMMIX model will use baseline hSBA titer as covariate and blood sampling time points at Visits 2, 3, and 4 as repeated dependent variables. The composite response

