### **6.3. Exploratory Endpoints**

#### **6.3.1. Bivalent rLP2086 Immune Response Exploratory Objectives**

Subjects in the Stage 1 evaluable immunogenicity population will be used for analysis. hSBA titers obtained 1 month after Dose 1 (Visit 2) will be descriptively summarized. The 5 coprimary endpoints will be reported similarly to the primary immunogenicity endpoint ([Section 6.1.1](#)).

Additionally, the proportion of subjects with hSBA titer  $\geq$  LLOQ for each MenB strain as well as hSBA titers  $\geq 1:4$ ,  $\geq 1:8$ ,  $\geq 1:16$ ,  $\geq 1:32$ ,  $\geq 1:64$ , and  $\geq 1:128$  will be summarized similarly as described in [Section 6.2.1.1](#). Descriptive statistics on the GMTs as defined in [Section 5.2.2.1](#) will also be provided.

The hSBA GMTs for each MenB strain at Visit 11 will be summarized in Groups 2 and 4 combined for 1 month after the booster vaccination. See [Table 20](#).

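### SAP 5.2.1.2 leaves a baseline titer equal to the LLOQ outside all three 4-fold response rules, so read literally it is coded as non-response

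*SAP*

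**What the plan says.** SAP 5.2.1.2 sorts subjects into three baseline categories for the 4-fold response: below the LOD; at or above the LOD but below the LLOQ; and a third introduced as "For subjects with a baseline hSBA of > LLOQ, a 4-fold response is defined as an hSBA titer of" at least 4 times the baseline titer. The response variable is missing only if the baseline or follow-up result is unavailable. It is 1 if a definition is met and "0, if the assay result does not meet 1 of the 3 definitions for a 4-fold response".

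The endpoint definition in SAP 3.1.1 differs: "For subjects with a baseline hSBA of $\geq$ LLOQ, a 4-fold response is defined as an hSBA titer of" at least 4 times baseline. SAP 3.2.1 agrees with 3.1.1. So does protocol Section 9.2.1, "For subjects with a baseline hSBA titer of \geq LLOQ, a 4-fold response is defined as an hSBA titer of" at least 4 times baseline, as do the Protocol Summary and both places in protocol Section 2 where the rule appears.

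SAP Section 2 allows the SAP to depart from the protocol but says that "any major modifications of the primary endpoint definition or its analysis will also be reflected in a protocol amendment". Neither change log lists a change to this rule.

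**The concern.** The three categories in 5.2.1.2 leave a gap at exactly the LLOQ. A baseline there is an observed value, so the missing-data rule does not apply, and the catch-all codes the subject 0. A genuine 4-fold responder would be counted as a failure against a fixed target.

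The location matters because 5.2.1.2 is the only section that states the 1/0/missing coding, and SAP Section 2 says the programming rules are based on the methods in the SAP. The same variable feeds other Stage 1 analyses:

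- the comparison of MenABCWY with bivalent rLP2086 (SAP Table 19);
- the Visit 2 analysis, where "The 5 coprimary endpoints will be reported similarly to the primary immunogenicity endpoint";
- the GLIMMIX sensitivity analysis in SAP 5.3.1, if triggered, where "The response variables are binary variables (composite response and 4-fold response) and a Logit link will be used".

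**Working it through.** **1. Where the two readings differ.** I coded both rules on a 2-fold titer grid (the grid is an assumption; LOD and LLOQ come from SAP Table 16) and compared every pair of baseline and follow-up titers. They disagree only when baseline equals the LLOQ and the follow-up titer is at least 4 × LLOQ:

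- A56, B24, B44: baseline 1:8, follow-up 1:32 or higher;
- A22: baseline 1:16, follow-up 1:64 or higher.

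In each such pair > gives 0 and ≥ gives 1.

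**2. Reproducing the plan's power.** Inputs are the targets and planning rates in protocol Table 12, n = 900 (global) and n = 748 (US, protocol 9.1), and two-sided 95% Clopper-Pearson limits. The needed count r is the smallest with BetaInv(0.025; r, n − r + 1) above the target. Power is P(X ≥ r) for X ~ Binomial(n, planning rate). Overall power is the product of the five.

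| Endpoint | Target | Planning rate | Needed, n=900 | Power, n=900 | Table 12 |
|---|---|---|---|---|---|
| A22 | 75% | 82.3% | 701 | 99.97% | 99.97% |
| A56 | 85% | 90.1% | 787 | 99.58% | 99.60% |
| B24 | 55% | 64.5% | 525 | 99.99% | 99.99% |
| B44 | 60% | 66.0% | 570 | 95.70% | 95.7% |
| Composite | 65% | 72.9% | 614 | 99.92% | 99.92% |
| Overall | | | | 95.19% | 95.2% |

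For n = 748 the product is 90.08%, against 89.9% stated. The planned figures are sound and are not in dispute.

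**3. Miscoded responders that would turn a pass into a fail.** With results at the planning rate, this is expected responders − needed + 1.

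| Strain | n | Expected | Needed | Miscoded to fail |
|---|---|---|---|---|
| B44 | 900 | 594 | 570 | 25 (2.8%) |
| A56 | 900 | 811 | 787 | 25 (2.8%) |
| A22 | 900 | 741 | 701 | 41 |
| B24 | 900 | 580 | 525 | 56 |
| B44 | 748 | 494 | 476 | 19 (2.5%) |
| A56 | 748 | 674 | 656 | 19 (2.5%) |

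These are counts of miscoded responders. The number of subjects with baseline at the LLOQ would have to be larger. For B44 at n = 900, if such subjects otherwise respond at 66% or 50%, the requirement is 25/0.66 ≈ 38 or 25/0.50 = 50 subjects, which is 4.2% to 5.6% of 900.

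**4. Illustration for B44 at n = 900.** The documents give neither the share of subjects with baseline at the LLOQ nor their response rate, so both are assumed. The response rate becomes 66.0% − share × (50% to 66%).

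| Share with baseline = LLOQ | B44 power |
|---|---|
| 0% | 95.7% |
| 1% | 90.3% to 91.9% |
| 2% | 81.1% to 86.1% |
| 3% | 68.0% to 77.9% |

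These figures show sensitivity. They do not estimate what happened.

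**The case against.** The strongest reply is that this is an erratum. Six other statements of the rule agree, so the intent is not in doubt. The correction needs no judgement either: when baseline equals the LLOQ, 4 × LLOQ and 4 × baseline are the same number. That all stands, and it makes the fix easy. It does not show what was programmed.

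A second reply is that the text may have had no practical effect:

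- **Stage 1 was already reported.** Of the fever scales, the SAP says the original one "was used in Stage 1 reporting and the updated temperature scale" applies to Stage 2.
- **An unseen SAP version may have governed Stage 1.** Protocol Amendment 2 (9 July 2019) already refers to Stage 1 analyses as performed. The latest SAP version before it in the log is version 3 (29 October 2018), which is not available here and whose wording of this rule is unknown.
- **No Stage 2 analysis depends on it.** Version 5 drops the 4-fold rise from Stage 2, and every use listed above is in Stage 1.
- **Programming rules are separate documents.** Nothing shows that any program used >.

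These points are fair and limit the likely impact. They also make the Stage 1 program the thing to check, because correcting the SAP alone would not settle what was run.

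A third reply is that the power illustration rests on assumed inputs and says little about a completed analysis. That is right. The useful quantity is the count of affected subjects.

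A symbol lost in PDF conversion cannot be excluded, but ≥ is rendered correctly elsewhere in the same bullet.

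**Conclusion.** The concern holds. As printed, 5.2.1.2 gives a wrong derivation rule for four of the five coprimary endpoints and contradicts SAP 3.1.1, SAP 3.2.1 and the protocol. It is probably a slip.

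If it was programmed, its only effect is to lower 4-fold rates. The risk is a wrongly missed criterion, most plausibly in B44 or A56, where the margin at the planning rates is 25 miscoded responders of 900, or 19 of 748 in the US analysis. Those margins assume results exactly at the Table 12 rates. The actual number affected is unknown; it may be zero, and would be near zero if titers are interpolated rather than reported in 2-fold steps. Type I error, the composite endpoint, the stated power and the sample size are unaffected. It should be fixed.

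**What to change.** Replace > with ≥ in the third baseline bullet of SAP 5.2.1.2, to match SAP 3.1.1 and protocol Sections 2 and 9.2.1. Check and document which rule the Stage 1 program applied.

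If it used ≥, nothing more is needed. If it used >, report for each strain how many subjects had a baseline equal to the LLOQ and how many of them had a follow-up titer of at least 4 × LLOQ. Then rerun the Stage 1 4-fold analyses: primary (global and US), the MenABCWY comparison, Visit 2 exploratory, and GLIMMIX if it was triggered.

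The cost is one character and one program check, with a rerun of the 4-fold analyses only in the second case.

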### 5.2.1.3. Safety Data

All safety endpoints (including reactogenicity data recorded from the e-diary and AE data recorded from the CRF) will be summarized with percentages and 95% exact CIs (Clopper-Pearson method) for each group. The difference in the percentages (Group 1 – Group 3) and 2-sided 95% CIs for the difference will be provided to compare the secondary endpoints of reactogenicity, AEs, SAEs, MAEs, NDCMCs, and immediate AEs. The CIs of the difference will be computed using the Miettinen-Nurminen method.

The CIs presented for the safety data will not be used to test hypotheses but will be used to determine which events may need further clinical investigation. No adjustment for multiplicity is needed.

## 5.2.2. Analyses for Continuous Data

### 5.2.2.1. Geometric Mean Titers

GMTs will be computed for each hSBA titer for MenB and MenA/C/W/Y strains. If the hSBA result is below LLOQ, it will be set to  $\frac{1}{2}$  the LLOQ for the GMT calculation. The assay results at each blood sampling time point will be (natural-log) logarithmically transformed for analysis. GMTs are obtained by log transformations of indicated values, averaging the log values, then exponentiating the result. The associated 2-sided 95% CIs will

be constructed by back transformation of the confidence limits computed for the mean of the logarithmically transformed assay results using Student's t distribution.

#### **5.2.2.2. School and Work Days Missed**

Days on which a subject missed school and/or work because of an AE will be captured on the AE checklist. The data captured at each visit will be summed and a total number of days obtained.

### **5.3. Methods to Manage Missing Data**

#### **5.3.1. Immunogenicity Data**

As assay data are expected to be missing completely at random, the primary analysis for the primary objectives will be based upon the observed, determinate observations. No imputation will be performed. The proportion of subjects with missing immunogenicity data may be summarized at each blood sampling visit for each primary MenB strain. The denominator will be the ITT population (all randomized). The category of missing reasons (quantity not sufficient [QNS], indeterminate, not done, dropout) may also be summarized. Similar summaries may also be performed to evaluate the proportion of missing hSBA-MenA, hSBA-MenC, hSBA-MenW, and hSBA-MenY titers.

If 10% or more of the subjects in any strata have missing hSBA data for the 4 primary MenB strains, a sensitivity analysis using mixed-effects model with repeated measures (MMRM) for Groups 2 and 4 will be applied for the primary MenB strains (GMT). The MMRM uses maximum likelihood estimation under the assumption that the missingness is at random (MAR). To account for the intrasubject correlation among the repeated measures, an unstructured covariance matrix will be used. In case the model does not converge, further covariance structures will be explored (ie, first-order autoregressive, compound symmetry).

$\text{Log (hSBA)} = \text{race} + \text{sex} + \text{geographic location (US; ex-US)} + \text{age at randomization} + \text{visit}$ .  
The intercept will be set as random effect.

Race categories other than White, Black, or Asian will be combined into a separate category termed "Other."

In addition to Type III analysis output, least-squares GMTs at each visit will be summarized for each strain.

These analyses will use the mITT population, using ½ LLOQ to impute the hSBA values below LLOQ for the primary strains only.

Similar to GMT, GLIMMIX will be utilized. The response variables are binary variables (composite response and 4-fold response) and a Logit link will be used. The model will be similar to the above. As 4 out of 5 endpoints (4-fold responses) will not have a response at Visit 1, the GLIMMIX model will use baseline hSBA titer as covariate and blood sampling time points at Visits 2, 3, and 4 as repeated dependent variables. The composite response

analyses will be similar to the GMT analyses, with composite responses at all 4 visits modeled as dependent variables. This analysis will only be applied to the mITT population. The model-estimated response rates and the 95% CI will be summarized for each of the 5 coprimary endpoints at each applicable time point.

For the hSBA assay results, the following values will be set to missing: QNS (insufficient sera), indeterminate results, and not done. Subjects without blood draws (ie, dropout) will also have missing data for immunogenicity.

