9.1. Sample Size Determination

Both hypothesis testing and estimation will be performed. The hypothesis-testing component will address the need to confirm the immunogenicity of bivalent rLP2086 administered at Months 0 and 6 in all subjects 10 through 25 years of age, using prespecified criteria for the primary MnB immunogenicity endpoints. Safety of bivalent rLP2086 administered at Months 0 and 6 will also be described. Immunogenicity and safety information for the MenABCWY arms will be described.

Hypothesis testing will be performed on the 5 coprimary MnB endpoints in all subjects, which will include a 4-fold rise from baseline in hSBA titers for each of the 4 primary strains and the composite response (hSBA titer \geq LLOQ for all 4 primary strains combined) 1 month after the second vaccination. If the lower limit of the 2-sided 95% confidence interval (CI) exceeds each of the target lower limit of the confidence interval (LCI) values, the study's primary objective will be met.

The null hypothesis will be that the true proportion of subjects is less than or equal to the target LCI criterion for 1 or more primary endpoints. The alternate hypothesis is that the true proportion of subjects for each of the primary immunogenicity endpoints exceeds the target LCI.

Hypothesis testing will be performed by calculating 2-sided 95% CIs on each of the 5 MnB endpoints limited to Groups 2 and 4 in which ACWY-naive and ACWY-experienced cohorts will be combined. The Clopper-Pearson method will be used to calculate the CIs for the proportions. If the LCI exceeds the corresponding target LCI for each strain and the composite, then the null hypothesis will be rejected.

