The study sample size is mainly based on hypothesis-testing criteria to verify the clinical benefit of a 2-dose schedule for the use of bivalent rLP2086 administered at Months 0 and 6 in healthy subjects 10 years to <26 years of age in both Group 2 and Group 4. Given the observed response proportions from Study B1971012 for each endpoint, with 900 evaluable subjects, the primary objective based on all 5 primary endpoints will be met with a power of 95.2% (Table 12). Furthermore, with 748 evaluable subjects from US sites, the LCI criteria for the primary objective will also be met with a power of 89.9%. For the global study, assuming that ~85% of enrolled subjects qualify for the evaluable immunogenicity population, ~1060 subjects should be enrolled to receive bivalent rLP2086 and MenACWY-CRM. This assumes that every subject has sufficient sera for the 4 hSBAs.

Table 12. Overall Power to Meet the Primary Objectives

	Primary Endpoint Test Strain (Variant)	LCI Criteria	Study B1971012 0- and 6-Month Responses With 95% Confidence Interval (%) ^a	Number of Evaluable Subjects	Power
hSBA titer fold rise ≥4 from baseline	PMB80 (A22)	LL of 95% CI >75%	82.3 (76.3, 87.3)	900	99.97%
	PMB2001 (A56)	LL of 95% CI >85	90.1 (85.1, 93.8)	900	99.60%
	PMB2948 (B24)	LL of 95% CI >55	64.5 (57.4, 71.1)	900	99.99%
	PMB2707 (B44)	LL of 95% CI >60	66.0 (58.9, 72.6)	900	95.7%
Composite response (hSBA titer ≥ LLOQ for all 4 primary strains combined)		LL of 95% CI >65	72.9 (65.9, 79.1)	900	99.92%
Overall power					95.2%

Abbreviations: hSBA = serum bactericidal assay using human complement; LCI = lower limit of the confidence interval; LL = lower limit; LLOQ = lower limit of quantitation.

a. The power calculation was based on Study B1971012 with a vaccine schedule of 0 and 6 months.

An additional 530 subjects will be enrolled in the MenABCWY-MenABCWY regimen. Assuming 85% evaluable subjects, there will be 450 evaluable subjects in this regimen. These subjects will be further split between ACWY-naive and ACWY-experienced strata.

Given 530 subjects receiving at least 1 dose of MenABCWY, the probability of observing at least 1 AE will be 93.0% with a true incidence of 0.5% (see Table 13).

Table 13. Probabilities of Detecting AEs at Specified Incidences

Sample Size	True Incidence of AE	Probability of at Least 1 AE
530	0.01%	5.2%
530	0.10%	41.2%
530	0.25%	73.5%
530	0.50%	93.0%
530	1.00%	99.5%

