## 2.2. Study Design

### 2.2.1. Description

This is a Phase 3, randomized, active-controlled, observer-blinded multicenter trial in which approximately 1590 subjects will be randomly assigned to receive either MenABCWY (Trumenba+meningococcal polysaccharide groups A, C, W-135, and Y tetanus toxoid conjugate vaccine [MenACWY-TT] reconstituted) and saline or bivalent rLP2086 and MenACWY-CRM. All subjects will be naïve to any meningococcal group B vaccine prior to enrollment.

Randomization will be stratified by prior vaccination history; approximately 795 ACWY-naïve subjects and 795 ACWY-experienced (having received 1 prior dose of vaccine containing 1 or more ACWY groups  $\geq 4$  years prior to the date of randomization) subjects will be enrolled.

Randomization will also be stratified by geographic region. Approximately 1320 subjects from United States (US) investigator sites and 270 subjects from ex-US countries will be randomized. Regional stratification will ensure sufficient population representation. The study is powered to meet the primary objective for immunogenicity based upon US subjects alone and additionally for the US and ex-US subjects.

The study will be conducted in 2 stages:

- Stage 1: comprises visits from study entry (Visit 1) through Visit 6. A pilot cohort consisting of 10 subjects 18 to <26 years of age will initially be enrolled and assigned to either Group 1 or 3, depending on prior vaccination history, and will receive MenABCWY at Vaccination 1. Seven days after the last pilot cohort subject has received MenABCWY, 7-day electronic diary (e-diary) and AE data will be summarized for review by the sponsor's independent review committee (IRC). No further enrollment will be permitted until review of these safety data is complete. If the IRC finds the safety data from the pilot cohort acceptable, enrollment will be opened to all ages and randomization groups, and the pilot cohort subjects will proceed in the study as planned. During Stage 1, the sponsor will be blinded to vaccine assignment beyond the completion of pilot cohort enrollment.

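### The missing-data sensitivity models in SAP 5.3.1 adjust for region but omit ACWY history, the randomisation factor that separates pooled Groups 2 and 4

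*SAP*

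**What the plan says.** Randomisation has two stratification factors. SAP 2.2.1 gives the first: "Randomization will be stratified by prior vaccination history; approximately 795 ACWY-naïve subjects and 795 ACWY-experienced". The next paragraph of that section gives the second, region (US, ex-US). Group 2 is the ACWY-naive and Group 4 the ACWY-experienced arm receiving bivalent rLP2086 with MenACWY-CRM, planned at 530 each (SAP Table 2). They are pooled for the primary objective.

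SAP 5.3.1 bases the primary analysis on observed results, on the expectation that assay data are missing completely at random. It then sets a condition for a sensitivity analysis: "If 10% or more of the subjects in any strata have missing hSBA data for the 4 primary MenB strains". The MMRM for log titer in Groups 2 and 4 has race, sex, geographic location, age at randomisation and visit, with a random intercept, and assumes data missing at random. For the binary coprimary endpoints a GLIMMIX is specified by reference: "The model will be similar to the above". The 4-fold endpoints add baseline titer as a covariate and use Visits 2, 3 and 4 as repeated outcomes; the composite uses all four visits. Both models are fitted in the mITT population. Neither has a term for ACWY history or for Group 2 versus Group 4.

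**The concern.** Missing at random is a statement conditional on what the model contains. ACWY history is a design factor and defines the two groups being pooled. If it predicts both who lacks a titer and how well subjects respond to the MenB component, a model without it can still be biased.

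The specification is also uneven. The trigger is worded by strata and one randomisation factor is in the model, but the other is left out without a reason.

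For the four 4-fold endpoints the GLIMMIX is the only model-based missing-data check. Other planned output would show only half of the problem. SAP 6.6.1 tabulates withdrawals and blood samples by randomised group, so unequal missingness would be seen. But MenB responses are summarised with the strata combined (SAP 6), and the subgroup list in SAP 6.5 omits ACWY history, so unequal response would not.

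**Working it through.** **1. The plan's own figures.** Protocol 9.1 states: "Hypothesis testing will be performed by calculating 2-sided 95% CIs on each of the 5 MnB endpoints limited to Groups 2 and 4". For each endpoint, find the smallest count whose Clopper-Pearson lower limit exceeds the target, take the exact binomial power at the assumed rate, and multiply the five (independence assumed).

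| Endpoint | Assumed rate / target (%) | Power, n = 900 | Power, n = 748 |
|---|---|---|---|
| A22 | 82.3 / 75 | 99.97% | 99.82% |
| A56 | 90.1 / 85 | 99.58% | 98.61% |
| B24 | 64.5 / 55 | 99.99% | 99.96% |
| B44 | 66.0 / 60 | 95.70% | 91.92% |
| Composite | 72.9 / 65 | 99.92% | 99.61% |
| Product | | 95.19% | 90.08% |

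The protocol gives 95.2% and 89.9%, so its figures reproduce closely. No sensitivity-model term enters this calculation.

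**2. Design factors against model terms.**

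| Factor | Randomisation stratum? | In MMRM and GLIMMIX? |
|---|---|---|
| Region | Yes | Yes |
| ACWY history (Group 2 vs 4) | Yes | No |
| Age | No (enrolment target only) | Yes |

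**3. Bias in the observed-case proportion.** Take two equal strata with missing fractions m2 and m4 and true response rates p2 and p4.

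Bias = [(1 − m2)p2 + (1 − m4)p4] / (2 − m2 − m4) − (p2 + p4)/2 = −(m4 − m2)(p4 − p2) / [2(2 − m2 − m4)]

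The bias is zero if either the missing fractions or the response rates are equal. The documents give neither by ACWY stratum, so every input below is an assumption. The rates are centred on the 66% assumed for B44.

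- Missing 10% / 20%, response 64% / 68%: −(0.10 × 4)/(2 × 1.70) = −0.12 points
- Missing 10% / 20%, response 61% / 71%: −(0.10 × 10)/(2 × 1.70) = −0.29 points
- Missing 8% / 22%, response 61% / 71%: −(0.14 × 10)/(2 × 1.70) = −0.41 points
- Extreme case, missing 0% / 30% with a 10-point gap: (0.30 × 10)/(2 × 1.70) = 0.88 points in size

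**4. What a model without the stratum would leave.** Step 3 describes observed cases, not the models. A small simulation used Gaussian log2 titers at an earlier visit and at Visit 4, n = 1060, SD 2 log2, 400 runs, and Visit 4 missing in 30% of one stratum and 0% of the other. The stratum difference was the same at both visits. A binary age term was either unrelated to stratum or strongly related to it. Results are bias in log2 units.

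| Difference, correlation, age related? | Observed cases | No stratum term | With stratum term | Removed without stratum term |
|---|---|---|---|---|
| 0.5, 0.5, no | −0.048 | −0.025 | −0.004 | 48% |
| 0.5, 0.5, yes | −0.040 | −0.011 | 0.003 | 72% |
| 0.5, 0.7, no | −0.044 | −0.014 | −0.002 | 68% |
| 0.5, 0.7, yes | −0.045 | −0.008 | 0.001 | 82% |
| 1.0, 0.5, no | −0.082 | −0.036 | 0.006 | 57% |
| 1.0, 0.5, yes | −0.093 | −0.033 | −0.005 | 65% |
| 1.0, 0.7, no | −0.091 | −0.027 | −0.002 | 70% |
| 1.0, 0.7, yes | −0.089 | −0.017 | −0.000 | 81% |

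The last column is 1 − (no stratum term / observed cases), taken before rounding. With no true stratum difference, all three estimators came within 0.009 of zero, which shows the simulation error; the results with the stratum term are therefore indistinguishable from unbiased. The simulation covers log titers only, not the logit models. If the strata differed only at Visit 4, the earlier visit would carry no information about the difference and recovery would be weaker.

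**5. Scale.** The approximate 95% half-width at n = 900, 1.96 × √[p(1 − p)/900], is 3.09 points at 66.0%, 2.90 at 72.9% and 1.95 at 90.1%. The gaps between assumed rates and targets run from 5.1 points (A56) to 9.5 points (B24).

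**The case against.** The SAP has a rationale for pooling. All subjects are MenB-naive at entry (6.2.1.2), and it describes the evaluable-population analyses as independent of ACWY history (4.5). If MenB response does not differ by ACWY history after the covariates, there is no bias, and no figure in the documents shows that it differs. That stands. But those statements explain why the groups are combined; they are not evidence of equal response, and a sensitivity model is the natural place to relax the assumption.

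Four stronger readings are tempting, and the documents do not support them.

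- *The models cannot correct a stratum imbalance.* They use repeated visits, age and, for the 4-fold endpoints, baseline titer, all of which can recover part of it.
- *The models were meant to check imbalance between ACWY strata.* The stated purpose is to move from missing completely at random to missing at random. The trigger is a level of missingness and can fire with equal rates. Its strata are undefined; region, and what SAP 6.5 calls age strata, are covered by the model.
- *These are the only missing-data checks.* SAP 6.4 plans a different handling of missing results for the composite, and SAP Table 17 repeats all five endpoints in the mITT population, although the repeat is still observed-case.
- *The trigger will probably be met because about 15% are expected to be non-evaluable.* That figure in Protocol 9.1 also covers ineligibility, out-of-window draws and protocol deviations, where titers may exist. No expected rate of missing titers is given.

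**Conclusion.** The omission is real, and its severity is low. One of the two randomisation factors, the one that separates the pooled groups, is missing from both sensitivity models while the trigger refers to undefined strata.

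Residual bias needs two conditions together: missingness and MenB response must both differ by ACWY history beyond the modelled covariates and earlier visits. Under the assumed inputs in step 3, the 10/20% and 8/22% cases give an observed-case bias of about 0.1 to 0.4 points, and in the simulated settings the models left only part of such a bias. Both are small against half-widths of 2.0 to 3.1 points.

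A reader might infer that the coprimary conclusion is at risk. It is not, on this ground: the Clopper-Pearson test, the sample size and the stated power do not use these models, and the sensitivity analysis is conditional and confined to the mITT population. What is at issue is how far that analysis can be relied on as a check.

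**What to change.** In SAP 5.3.1:

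1. State that the strata in the trigger include both randomisation factors, ACWY history and region.
2. Add ACWY stratum and stratum-by-visit to the MMRM and to the GLIMMIX for the 4-fold and composite responses.
3. Use one definition of stratum throughout, for example true ACWY history as handled in SAP 4.5. Average the Visit 4 estimates over the mITT stratum proportions under that same definition. Weighting true-history strata by the planned 530:530 would mix two definitions, because SAP 4.5 reassigns mis-stratified subjects and counts unknown history as experienced.

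The statistical cost is one parameter for stratum plus one fewer than the number of visits for the interaction: four with four visits, three with three, against about 1060 subjects. The primary analysis does not change.

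There is a procedural cost. SAP 3.5.2.2 shows that Stage 1 has already been reported, so any rerun with these terms must be labelled a supplementary analysis and shown beside the model as specified, not in its place.
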